patients on a weekly basis or even monthly basis. The personal coaching aspect of Kurbo is expected to improve outcomes by increasing user access to feedback and advice.

A Pilot Study to Assess the Compliance and Impact on Weight of Kurbo, a Pediatric Centered Weight Loss App

Clinical Trials ID NCT02880254

Specific Aims

The purpose of this pilot study is to assess the feasibility, compliance with and effects of a pediatric centered weight loss app on BMI z-scores in a group of children and adolescents in a pediatric weight management program. We will assess the impact of the app as an adjunct to current weight management therapy, both with and without the personal health coach (PHC) option. We propose the following primary specific aims.

Primary Specific Aims & Hypotheses

1. The **Primary aim** is to assess 3 month compliance with the Kurbo app as well as the Kurbo app and PHC by a group of morbidly obese children and adolescents in a weight management program.
 - a. We hypothesize that compliance with the Kurbo app and Kurbo app plus PHC will be better than known compliance of our standard of care group.
2. The **Secondary aim** is to assess the effect of the Kurbo app as well as the Kurbo app and PHC on 3 month change in BMI-z score among morbidly obese children and adolescents undergoing a weight management program.
 - b. We hypothesize that the use of the Kurbo app and Kurbo app plus a personal health coach will result in a greater reduction in BMI z-score over 3 months than known change in our standard care group.
 - c. We hypothesize that the use of the app and personal health coach will result in a greater reduction in BMI z-score over 3 months than with the use without the personal health coach.

A Pilot Study to Assess the Compliance and Impact on Weight of Kurbo, a Pediatric Centered Weight

Loss App

Clinical Trials ID NCT02880254

Methods

Study Design: We wish to establish that Kurbo and/or Kurbo + PHC have better compliance and/or change in BMI-z scores than our current standard of care. To do this we will use two single arm studies, where subjects will be randomized into either group; however, each will be compared to our known standard. Assuming that we can establish better compliance and/or change in BMI-z score, we will also generate descriptive estimates using a parallel randomized trial design comparing the two groups (Kurbo vs. Kurbo + PHC).

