
Follow-Up: As part of standard of care, subjects will be seen every 4-6 weeks during their regularly scheduled weight management appointments to assess height, weight, and to calculate BMI. The subject will meet with a dietitian for further guidance and recommendations at baseline and the end of the study (approx. 3 months) and will meet with the physician for a routine exam at each visit as per standard of care in our pediatric weight management program. In addition to standard of care, at each visit subjects will complete the questionnaire as described above. Branching logic will be used within REDCap to direct appropriate questions to subjects with or without the PHC. The questionnaire is designed to assess compliance (see measures section). A separate survey will be used at the final visit; however the same survey procedures will be followed. During the 3 month study window we expect up

to 4 time points (baseline, months 1, 2 and 3(the final visit). If visits do not fall every 4 weeks, then fewer interim data points will be collected.

Measures: We will gather data from a variety of sources including EMR documentation (for standard of care visits) as well as subject surveys.

Exposure: Using the two-single arm study design, we will compare Kurbo vs. our known standard and Kurbo + PHC vs our known standard. Our standard of care estimates are based on existing data from a 6 month Baystate pediatric weight management spinoff called MIGHTY. Both MIGHTY and Kurbo could be considered augmented programs that spin off of our pediatric weight management program. MIGHTY stands for Moving, Improving, and Gaining Health Together at the YMCA. It is an intensive six-month group program that emphasizes physical activity, nutrition, and change of habits for the entire family. It includes a fitness evaluation, individual fitness prescriptions, group exercise sessions, individual and group nutritional counseling as well as strategies for maintaining lifelong health. Families who participate in MIGHTY receive a free six-month membership to the Springfield YMCA. Children interested in enrolling in MIGHTY must first be evaluated through our Pediatric Weight Management Program. Estimates from this program will be adapted for our power calculations.

If we can establish that Kurbo is better than our known standards, then we will estimate differences between Kurbo vs. Kurbo + PHC. Group assignment will be randomized in a 1:1 ratio using random permuted blocks.

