To assess our hypotheses we will utilize one-sample tests with a one-sided alpha of 0.025. One-sided tests will be used as we are only interested in whether the use of this app results in better outcomes than usual care. Compliance will utilize a binomial probability test to assess compliance (calculated over 3 months) against our known compliance of 50%. BMI-z score change (absolute change from baseline to 3 months) will utilize a one-sample t-test to assess observed BMI-z score change at 3 months against our estimated change of a 1% decrease. We will present our findings graphically, along with point estimates and one-sided 97.5% confidence intervals.

Assuming we find improved compliance and BMI-z scores, we will also estimate compliance and BMI-z score differences between Kurbo and Kurbo + PHC. Estimates will be generated using direct observation as well as prediction through modeling (e.g. GEE, linear mixed models). As data will be collected monthly, we will also describe changes over time and any possible dose-response effects. We will also evaluate possible differences in effects based on age category stratification (10-14 yrs and 15-17 yrs). We will present our findings graphically, along with 95% confidence intervals. These results may be used to inform study design and power calculations for a future study assessing differences between Kurbo and Kurbo + PHC as well as changes in obesity-related comorbidities.

Power and Sample Size: Studies in pediatric and adult weight management trials indicate that the attrition rate is poor (4, 6, 8) as well as unpublished data from our pediatric weight management spin off program, MIGHTY, indicate that 6 month compliance (attendance) is close to 50% and 6 month change in BMI-z scores is approximately a 2% decrease with a change standard deviation (SD) of 0.12. As described in our data analysis section, we will estimate compliance to be 50% and BMI-z decrease 1%. We will keep the same SD of 0.12. Sample size calculations assume a one-sided alpha of 0.025, and power of 0.80.

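### Hypothesis 2c is unconditional, but the randomised Kurbo + PHC versus Kurbo contrast that answers it is planned only if an external standard is first beaten, under a condition worded differently in each section

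*Combined protocol and SAP*

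**What the plan says.** Under Primary Specific Aims & Hypotheses, item 2, hypothesis c reads "We hypothesize that the use of the app and personal health coach will result in a greater reduction in BMI z-score over 3 months" than without the coach. No condition is attached.

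Four places in Methods plan the between-arm contrast, and all make it conditional on first beating a standard derived from the MIGHTY programme:

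- **Study Design:** "Assuming that we can establish better compliance and/or change in BMI-z score, we will also generate descriptive estimates using a parallel randomized trial design". The opening aim there is to show that "Kurbo and/or Kurbo + PHC have better compliance and/or change in BMI-z scores than our current standard of care".
- **Measures, Exposure:** "If we can establish that Kurbo is better than our known standards, then we will estimate differences between Kurbo vs. Kurbo + PHC". The same paragraph uses Kurbo for one arm ("we will compare Kurbo vs. our known standard and Kurbo + PHC vs our known standard") and for the programme as a whole ("Both MIGHTY and Kurbo could be considered augmented programs that spin off of our pediatric weight management program").
- **Data Analysis:** "Assuming we find improved compliance and BMI-z scores, we will also estimate compliance and BMI-z score differences between Kurbo and Kurbo + PHC".
- **Power and Sample Size:** the contrast is introduced as something the study may progress to, with no criterion. It is sized for d = 0.50, two-sided alpha 0.05, power 0.80, four measures and correlation 0.3, giving about 28 per group.

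Independently of any condition, Data Analysis promises descriptive statistics including means and SDs, and for the one-sample comparisons "point estimates and one-sided 97.5% confidence intervals".

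**The concern.** The one-sample tests assigned to the hypotheses compare each arm with a fixed external value, so none of them can address 2c. The analysis that can is allowed to drop out, and the sections disagree on when. *Either or both* and *both* are different decision rules. No version of the condition says which arm must succeed, or whether success means a significant test or merely a better point estimate.

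At stake are the between-arm difference with its 95% CI, the modelled estimate and the within-subject correlation. Data Analysis wants these results for planning a later comparison of the two arms, and the power section says no estimates of variability or correlation over time are yet available. A team that follows one section could omit the contrast where a team that follows another would report it, and that choice would be made with the results in view.

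**Working it through.** **1. The plan's own figure.** With one baseline and three follow-up measures analysed by repeated-measures ANCOVA, n per group = 2(z₀.₉₇₅ + z₀.₈₀)²/d² × [(1 + 2ρ)/3 − ρ²]. With (1.960 + 0.842)² = 7.849, d = 0.50 and ρ = 0.3, this is 62.79 × (0.5333 − 0.09) = 27.8, so 28 per group, as stated. Allowing 20% withdrawal, 28/0.80 = 35. The sizing of the contrast reproduces.

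**2. Inputs for the condition (Data Analysis; Power and Sample Size).** Compliance 75% against 50%; BMI-z decrease 5% against 1% of 2.267, a shift of 0.04 × 2.267 = 0.0907; SD 0.12; one-sided alpha 0.025.

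Assumptions of this check: success means a significant test; compliance is counted yes/no per child (the Outcomes section gives no cut-off); the two outcomes are independent; 30 per arm, with 28 shown as what remains of 35 after 20% withdrawal.

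**3. Probability that one arm passes one test** (exact binomial; noncentral t).

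| | n = 30 | n = 28 |
|---|---|---|
| Compliance rejects at | ≥ 21 | ≥ 20 |
| Pass if true compliance 75% | 0.803 | 0.750 |
| Pass if true compliance 50% | 0.0214 | 0.0178 |
| BMI-z pass if true decrease 5% | 0.979 | 0.971 |
| BMI-z pass if true decrease 1% | 0.025 | 0.025 |

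**4. Probability that the contrast is run.** Let c and b be an arm's pass probabilities for compliance and BMI-z, with subscript 1 for the app alone and 2 for the app with coach.

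- Reading A (any outcome, any arm): 1 − (1 − c₁)(1 − b₁)(1 − c₂)(1 − b₂).
- Reading B (both outcomes in at least one arm): 1 − (1 − c₁b₁)(1 − c₂b₂).

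| Truth | A, n = 30 | B, n = 30 | A, n = 28 | B, n = 28 |
|---|---|---|---|---|
| Both arms at the plan's targets | > 0.999 | 0.95 | > 0.999 | 0.93 |
| Only the coach arm works | 0.996 | 0.79 | 0.99 | 0.73 |
| Coach 5%, app 1%, compliance 50% in both | 0.98 | 0.02 | 0.97 | 0.02 |

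Example, first row under B at n = 30: c × b = 0.803 × 0.979 = 0.787, and 1 − (1 − 0.787)² = 0.95.

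**5. Sensitivity of the last row at n = 30.**

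- Coach compliance 65% or 70%, app 50%: B rises to 0.35 or 0.58.
- Data Analysis read outcome by outcome, so that BMI-z success in either arm releases the BMI-z contrast: 1 − (1 − 0.025)(1 − 0.979) = 0.98.
- A better point estimate counts as success: P(more than 15 of 30 | 50%) = 0.428. B is then 1 − (1 − 0.428)(1 − 0.428 × 0.5) = 0.55, and A is about 1.0.
- Any dependence between outcomes: A is at least 0.979, since the coach arm's BMI-z test suffices alone. B is at most 2 × 0.0214 = 0.043, since some arm must pass compliance.

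**6. Precision if the contrast is always reported.** The crude BMI-z half-width is t₅₈ × SD × √(2/30). At SD 0.12 it is 2.002 × 0.12 × 0.258 = 0.062; at the plan's upper SD of 0.14 it is 0.072.

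**The case against.** The strongest defence is that this is a pilot with a stated sequence: beat the standard first, then describe the difference between arms. Ordering a secondary descriptive comparison in this way is a legitimate choice. That stands, but it does not explain an unconditional 2c, nor conditions that differ between sections. A descriptive estimate also makes no confirmatory claim that a condition would need to protect.

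A second defence is that the Data Analysis sentence can be read in parallel, each outcome releasing its own contrast. That agrees with Study Design and removes the 0.02. The reading is fair, but the text does not settle it. Equally, reading B is assembled from Data Analysis and Study Design; no single section states it.

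Third, little is lost, because per-arm means, SDs and one-sample estimates are reported in any case and the monthly data are collected regardless. This is largely right. A crude difference could be derived, although the plan does not commit to reporting it.

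Stronger readings are tempting. A reader might infer that all four tests must succeed, or that the app-alone arm must meet both outcomes; no section says so. A reader might also infer that variability is hidden behind the condition, but SDs are reported unconditionally. Nor is the sample size of the contrast at fault, since 28 and 35 per group reproduce.

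**Conclusion.** The point holds as a fault of planning and internal consistency. A stated secondary hypothesis can go unanalysed under the plan, and whether it does depends on which section is followed. The contrast's status, descriptive or powered, is also unresolved.

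At the plan's targets the practical difference is small: above 0.999 against 0.95, or 0.93 after the planned withdrawal. It is moderate if only the coach arm works (0.996 against 0.79). It is large only when the two outcomes diverge. The 0.98 against 0.02 should not be taken as the typical effect: it needs the joint reading of Data Analysis, a significant test as the criterion, and true compliance of 50% in both arms. All compliance figures rest on an assumed yes/no measure. The direction does not depend on independence, because the either-outcome condition is never harder to meet than the both-outcomes condition.

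**What to change.** Delete the condition in Study Design, Exposure, Data Analysis, and Power and Sample Size. Always report Kurbo + PHC minus Kurbo for app compliance and for 3-month BMI-z change, each with a 95% CI, using the repeated-measures model already planned.

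Give the contrast one status throughout. Either keep 2c as a secondary hypothesis and test it at the two-sided 0.05 already used in the power section, or reword 2c as an estimation objective and call the contrast descriptive in the power section too. Relabelling the contrast alone would leave 2c a directional hypothesis without a test.

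If the sponsor prefers to keep a sequence, the lesser remedy is to state one condition (arm, outcomes, test or point estimate), use it in all four places, and word 2c to match.

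The cost is wording and a small analysis, with no extra subjects or data. The estimate may be imprecise, with the crude half-widths given above, and should be presented as such.

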In regards to compliance, we feel that to be of clinical importance we would want to observe close to 75% compliance with the Kurbo app and/or Kurbo + PHC. With a sample of 30 subjects in each Kurbo group (60 total), we would be able to conduct a one-sided, one-sample test against 50% compliance if we observe at least 75% compliance in our study groups (a 25% improvement in compliance). Larger samples would be required to test a smaller effect size (e.g. nearly 50 subjects per group would be required to test 70% compliance against 50%) and with the same sample size power would drop to 0.59 to test a 20% difference.

In regards to BMI-z score change, we feel that to be clinically relevant we would want to observe at least a 5% decrease (BMI-z score at baseline=2.267 vs. 3 months=2.154) in BMI-z score over a 3 month period

with the Kurbo app and/or Kurbo + PHC. With a sample of 12 subjects in each group, we would be able to conduct a one-sided, one-sample t-test against a 1% decrease assuming a standard deviation of 0.12 if we observe at least a 5% decrease in BMI-z score in our study groups. Effect sizes greater than the 4% difference described above will be picked up by this sample size. However, in the case that we have underestimated the SD, the upper limit of the 95% confidence interval is 0.14. With this SD we would need 19 subjects to detect this same effect.

If we progress to a comparison between Kurbo vs. Kurbo + PHC, we will utilize a repeated measures model such as GEE or linear mixed models. As we have no preliminary estimates of variability or correlation over time, we have estimated the sample required for a medium effect size of 0.50 (Cohen's d, calculated as the difference between means divided by the pooled standard deviation) assuming a two-sided alpha of 0.05, power of 0.80 and 4 repeated measures with a correlation of 0.3. In this case, we would need to sample balanced groups of approximately 28 each. If the correlation increases (e.g. 0.5 or 0.7) power will increase.

Based on the above information, in addition to adding ~20% for possible study withdrawal, we wish to recruit a total of 35 subjects in each Kurbo group for a total sample size of 70 subjects. This sample size should allow us to assess clinically relevant outcomes with sufficient power.

A Pilot Study to Assess the Compliance and Impact on Weight of Kurbo, a Pediatric Centered Weight

Loss App

Clinical Trials ID NCT02880254

Risks and Benefits

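### BMI-z: 12 per group gives about 67% power, and 80% needs 16. Compliance: 35 per group less 20% withdrawal leaves 28, below the 30 the plan requires.

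*Combined protocol and SAP*

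**What the plan says.** All the figures are in Methods, Power and Sample Size. The common settings are given once: "Sample size calculations assume a one-sided alpha of 0.025, and power of 0.80".

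- **BMI-z (secondary aim).** The SD of change is 0.12. The reference is a 1% decrease and the target a 5% decrease, from 2.267 to 2.154. The plan states "With a sample of 12 subjects in each group, we would be able to conduct a one-sided, one-sample t-test against a 1% decrease", and adds "Effect sizes greater than the 4% difference described above will be picked up by this sample size". For a pessimistic SD of 0.14 it says "With this SD we would need 19 subjects to detect this same effect".
- **Compliance (primary aim).** Thirty per group are required for a one-sided, one-sample test of 75% against 50%. With the same 30, power is said to fall to 0.59 for 70% against 50%. Data Analysis specifies a binomial probability test.
- **Recruitment.** The section ends: "in addition to adding ~20% for possible study withdrawal, we wish to recruit a total of 35 subjects in each Kurbo group", and concludes "This sample size should allow us to assess clinically relevant outcomes with sufficient power".

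**The concern.** The BMI-z section names the test, alpha, power, SD and both means, so its sample size can be checked directly. Twelve looks too small for a t-test at a standardised difference of about 0.76. The 12 and the 19 are also said to be for the same effect, yet the required size should scale roughly with the variance, and 19 × (0.12/0.14)² is about 14.

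For compliance, the withdrawal allowance does not return the number that the primary test needs. The closing claim of sufficient power therefore fails under the plan's own withdrawal rate, unless withdrawn subjects stay in the analysis. The plan does not say whether they do.

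At stake is whether the stated power can be relied on for the primary outcome, and whether a reader is misled about how few BMI-z completers would be enough. Falling from 35 to 12 is a loss of 23/35 = 66%; falling from 35 to 16 is a loss of 19/35 = 54%.

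**Working it through.** **BMI-z inputs.** One-sided alpha 0.025, power 0.80, SD 0.12 (sensitivity 0.14), one-sample t-test, 5% versus 1% decrease.

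- Difference from the percentages: 0.04 × 2.267 = 0.0907.
- Difference from the rounded means (2.25 at 3 months under the reference in Data Analysis, 2.154 under the target): 0.096. This is the larger of the two and so the more favourable to the plan.

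Power is P(T > t₀.₉₇₅,ₙ₋₁), where T is noncentral t with n − 1 degrees of freedom and noncentrality d√n, and d = difference/SD.

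| Difference | SD | d | Power at n = 12 | Smallest n for 80% (power) |
|---|---|---|---|---|
| 0.0907 | 0.12 | 0.756 | 0.665 | 16 (0.806) |
| 0.096 | 0.12 | 0.800 | 0.714 | 15 (0.821) |
| 0.0907 | 0.14 | 0.648 | – | 21 (0.806) |
| 0.096 | 0.14 | 0.686 | – | 19 (0.807) |

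The 19 reproduces with the rounded means, but the 12 does not reproduce with either difference. Two departures from the plan come close to 12:

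- a normal approximation gives 14 (difference 0.0907) or 13 (0.096), but the plan names a t-test;
- a t-test at one-sided 0.05 gives 13 or 12, but the plan names 0.025.

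No single choice gives both figures. At alpha 0.025 the t-test needs exactly 12 (SD 0.12) only for differences of 0.1067 to 0.1125. It needs exactly 19 (SD 0.14) only for 0.0952 to 0.0981. The ranges do not overlap.

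The difference detectable with 80% power at n = 12 is 0.889 × 0.12 = 0.1066. That is 0.1066/2.267 = 4.7 percentage points, not 4.

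At 28 completers BMI-z power is 0.97 (0.91 with SD 0.14), taking the smaller difference.

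**Compliance inputs.** Null 0.50, alternative 0.75, exact binomial test, one-sided 0.025. The critical count is the smallest one with null tail probability of at most 0.025.

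The plan's own figures come first. At n = 30 the critical count is 21 and the attained alpha 0.0214. Power is 0.803 at 75% and 0.589 at 70%. Both the 30 and the 0.59 reproduce, so the method is not in doubt.

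Withdrawal arithmetic:

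- 30 × 1.2 = 36.
- 30/0.8 = 37.5, so 38 per group to retain 30.
- 35 × 0.8 = 28.
- Retaining 30 of 35 tolerates 5/35 = 14.3% withdrawal.

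The 35 equals 28/0.8, and 28 is the size given for the comparison of the two app groups. The 35 may come from there, but that is an inference.

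Exact power at 75% versus 50%, by number evaluable:

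| n | 28 | 29 | 30 | 31 | 32 | 33 | 34 | 35 |
|---|---|---|---|---|---|---|---|---|
| Power | 0.750 | 0.713 | 0.803 | 0.771 | 0.737 | 0.819 | 0.789 | 0.858 |

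In this range only 30, 33 and 35 reach 0.80.

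**The case against.** **The BMI-z error changes nothing in practice.** BMI-z is the secondary aim, nobody proposes to run the study with 12, and 28 completers are ample. This stands: it is an error of reporting, not an underpowered endpoint. The figure is still wrong on its own inputs and inconsistent with its neighbour.

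**The withdrawal allowance is nearly rounding.** The plan says about 20%, and 35 is one short of 36. That excuses the wording. It does not alter the result that 20% withdrawal from 35 leaves fewer than the 30 the plan asks for.

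**Withdrawn subjects might stay in the denominator.** Compliance in the reference programme is attendance, so a subject who withdraws could reasonably count as non-compliant. The test would then keep n = 35, and power is 0.858 if 75% is the overall rate. This is a fair point, and it makes the 0.750 conditional. But an allowance for withdrawal presupposes that those subjects are lost from the test. Nor does keeping them necessarily rescue power. As an illustration, assume 75% compliance among completers and 20% withdrawn and counted as failures: the overall rate is 0.8 × 0.75 = 60%, and power at n = 35 is about 0.20.

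**Part of the drop from 0.80 to 0.75 is binomial discreteness.** This is true. Thirty is a local peak, 32 evaluable have less power than 28, and a normal approximation at 28 gives 0.786. The range of power should therefore be reported, not a single threshold.

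**Conclusion.** The concern holds in both parts. The BMI-z size of 12 is wrong under the stated test, alpha, SD and difference. Its power is 0.665 to 0.714, and 15 or 16 per group are needed, depending on whether the rounded means or the percentages define the difference. It does not drive enrolment.

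The compliance part matters more because it concerns the primary aim, though the shortfall is modest: two subjects per group, and power of 0.750 instead of 0.80. That figure assumes that 20% withdraw, that they leave the denominator, and that true compliance is 75%. Across 28 to 35 evaluable, power runs from 0.71 to 0.86.

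**What to change.** In Power and Sample Size:

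1. Restate the BMI-z sizes as 16 per group (SD 0.12) and 21 per group (SD 0.14). Alternatively, declare the difference as 0.096 and give 15 and 19. Either way, both figures come from one calculation.
2. State that 35 per group with 20% withdrawal leaves 28 evaluable, and that compliance power is then 75% if withdrawn subjects leave the denominator. State that 30 evaluable give 80%, and that exact binomial power ranges from 71% to 86% for 28 to 35 evaluable.
3. State how withdrawn subjects are counted in the compliance test.

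The total of 70 and both tests stay as they are. The cost is corrected text in one section, and a slightly less favourable power statement for the primary outcome.

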A Pilot Study to Assess the Compliance and Impact on Weight of Kurbo, a Pediatric Centered Weight Loss App
Clinical Trials ID NCT02880254
Outcomes

Compliance: The compliance measure from our known standard (MIGHTY program) is showing up for a visit (e.g. attendance). As comparable measures, we will define compliance with Kurbo app to be daily use for tracking food intake, exercise, accessing the app features (games, badges). Surveys will have specific questions such as: "Over the last month, how many days per week do you usually use Kurbo to track food?" A summary compliance score will be calculated as follows: we expect subjects to use Kurbo to track food daily (7 days per week). Over the 3 follow-up study visits, if a subject responds to the above question with a 7, 5 and 6, we will take the average of this and divide it by the expected. In the above example: $18/3 = 6$ and $6 / 7 = 85.7\%$ compliant. Expected compliance for using Kurbo to track exercise = 7 days. There is no expected compliance for the use of games and obtaining badges.

Compliance with the PHC will be assessed based on the subjects' ability to have these meetings at least once a week. In order to collect this information we will ask "Over the last month, how many total meetings have you had with your personal health coach?" Compliance will be assessed in the same way as defined above with the expected compliance of 4 times in the last month. Use of the coaching feature will be defined as a complete phone or video conference. We will also assess the number of times they needed to reschedule these PHC visits.

BMI-z score: This is standard of care data that is recorded in PEDRO. The research coordinator will gather relevant BMI-z score data from PEDRO and enter it into REDCap for all study visits.

Covariates: We will collect the following from the EMR (age (yr, mo), height (cm), weight (kg), insurance category (private vs public), sex, race, and ethnicity). We will also ask subjects what their current grade level is.

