Study Timeline: We plan to recruit 70 subjects within the first 6 months of protocol acceptance. With nearly 22 new patients a week we do not anticipate that recruitment will take longer than 2 months, however we will leave our recruitment window open for 6 months at which time we will close recruitment, even if we have not accrued 70 subjects. As the Kurbo intervention is 3 months in duration, we expect the full implementation of this study to last approximately 9 months. Data analysis will be initiated by the EBRC at the completion of data collection. We anticipate analysis to take 3 months.

Prior Studies and Feasibility: As this is a pilot study, no preliminary studies have been conducted in support of this study. We anticipate timely recruitment given the high volume of new patients in our weight management clinic. In order to establish feasibility for a larger study, we will measure participant compliance and other feasibility measures with this pilot study.

The Principal Investigator has experience in conducting retrospective trials, drug treatment trials, prospective and randomized controlled trials during her time at Baystate as well as during her fellowship. Other members of the team, including the research coordinator and other providers, have also had some research experience in retrospective and prospective randomized controlled trials.

Data Analysis: We wish to evaluate two outcomes (compliance and BMI-z score change) among two groups (Kurbo and Kurbo + PHC). To do this we will use two single arm studies, where subjects will be randomized into either group, however each will be compared to a known standard. In this case, the known standards (based on existing data from our usual care group) are based on a 6-month compliance rate of 50% and a BMI-z score decrease near 2% (BMI-z score at baseline=2.27 vs. 6 months=2.22). To adapt these to a 3-month intervention, we feel that compliance at 3 months will remain the same (50%) and BMI-z change will be around 1% (BMI-z score at baseline=2.27 vs. 3 months=2.25).

Upon completion of the study, data will be inspected for outliers and logic checks will be conducted. Initial results will include means, standard deviations, medians and ranges for continuous measures and frequencies and percentages for categorical measures. Graphical representations will be utilized as needed.

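### The 20% withdrawal allowance leaves 28 evaluable per arm, where the primary compliance test has power 0.75 rather than the stated 0.80, and no basis is given for the 20%

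*Combined protocol and SAP*

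**What the plan says.** All references are to the combined protocol and SAP.

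- **Error rates.** Under Data Analysis, "we will utilize one-sample tests with a one-sided alpha of 0.025". Under Power and Sample Size, "Sample size calculations assume a one-sided alpha of 0.025, and power of 0.80".
- **Primary test.** Data Analysis: "Compliance will utilize a binomial probability test to assess compliance (calculated over 3 months) against our known compliance of 50" per cent. Power and Sample Size begins the compliance calculation "With a sample of 30 subjects in each Kurbo group (60 total") and takes 75% as the alternative. It adds that power falls to 0.59 at the same size if the true figure is 70%.
- **Between-arm comparison.** The same section asks for about 28 per group (d = 0.50, four measures, correlation 0.3).
- **Recruitment.** "in addition to adding ~20% for possible study withdrawal, we wish to recruit a total of 35 subjects in each Kurbo group", 70 in all. The section ends by calling this enough for the clinically relevant outcomes, without qualification.
- **The 50% figure.** Outcomes, Compliance: "The compliance measure from our known standard (MIGHTY program) is showing up for a visit (e.g. attendance"). Data Analysis carries the six-month figure to the trial's horizon: "we feel that compliance at 3 months will remain the same (50" per cent).
- **Data collection.** Follow-Up: "at each visit subjects will complete the questionnaire as described above". The Randomization, Allocation and Blinding section has the survey opened on a hospital PC at a scheduled visit. BMI-z is abstracted from standard-of-care visit records. No off-site survey, app-log source for compliance or rule for missed visits is described.

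**The concern.** There are two separate problems.

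The first is internal to the sample size section. The allowance for loss and the power claim do not fit together: 20% off 35 gives the number required for the conditional between-arm comparison, not the number required for the primary aim.

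The second is the allowance itself. The section refers to poor attrition in weight-management studies and to attendance near 50% in MIGHTY, then allows about 20% without saying why. A child who stops attending gives no further survey and no three-month BMI-z, so evaluable numbers depend directly on attendance. If loss exceeds 20%, the primary test is the first to suffer.

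**Working it through.** **Inputs.** Null 50%, alternative 75%, one-sided alpha 0.025, target power 0.80, 30 evaluable and 35 recruited per arm, about 20% loss (Data Analysis; Power and Sample Size). Each child counts as one compliant/non-compliant result, as the plan's calculation implies.

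**Method.** For each n, take the smallest r with P(X ≥ r | n, 0.50) ≤ 0.025. Power is P(X ≥ r | n, 0.75).

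**Reproducing the plan.** At n = 30, r = 21, attained alpha is 0.0214 and power is 0.803. With a true rate of 70%, power is 0.589. These match the stated 0.80 and 0.59, so this is evidently the plan's method.

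**The allowance.**
- 35 × (1 − 0.20) = 28.
- 28 / (1 − 0.20) = 35 exactly, so 35 fits the between-arm requirement.
- 30 / (1 − 0.20) = 37.5, so keeping 30 would take 38 per arm.
- 1 − 30/35 = 0.143, so 35 tolerates about 14% loss.

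**Compliance power by loss from 35.**

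| Loss | Evaluable n | r | Attained alpha | Power |
|---|---|---|---|---|
| 14% | 30 | 21 | 0.0214 | 0.803 |
| 20% | 28 | 20 | 0.0178 | 0.750 |
| 35% | 22 | 17 | 0.0085 | 0.517 |
| 35% | 23 | 17 | 0.0173 | 0.654 |
| 50% | 17 | 13 | 0.0245 | 0.574 |
| 50% | 18 | 14 | 0.0154 | 0.519 |

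Two rows appear where 35 × (1 − loss) is not whole (22.75 and 17.5). Exact power moves in steps with n because r is a whole number, which is why 17 does better than 18.

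**If 50% means visits missed independently.** A child seen at any one of three follow-up visits gives some score: 35 × (1 − 0.5³) = 30.6, about 31. At n = 31, r = 22 and power is 0.77.

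**Between-arm comparison at 17 to 18 per arm.** Power = Φ(0.5 / √(2f/n) − 1.96), where f is the variance factor.
- Mean of four measures: f = (1 + 3 × 0.3)/4 = 0.475. This requires about 30 per arm for 0.80, and gives 0.56 to 0.59 at 17 to 18.
- Mean of three follow-up measures adjusted for baseline: f = (1 + 2 × 0.3)/3 − 0.3² = 0.443. This reproduces the plan's 28 (power 0.80), and gives 0.59 to 0.62 at 17 to 18.

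**BMI-z at 17 to 18 per arm.** The difference is (5% − 1%) × 2.267 = 0.0907. One-sample t power is 0.83 to 0.86 at SD 0.12 and 0.71 to 0.74 at SD 0.14. (The plan's figure of 12 per group at SD 0.12 does not reproduce this way: power at 12 is 0.67, and 16 are needed. That is a separate matter.)

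**The case against.** A reader might infer that the plan itself assumes 50% attendance at three months, so that 17 to 18 evaluable is its own prediction and contradicts the 20%. The documents do not support this. The 50% is the MIGHTY benchmark and serves as the null; nowhere is it the expected attendance of Kurbo participants. MIGHTY is an intensive six-month group programme, whereas this study adds an app to routine clinic visits over three months. Children are also approached at their second appointment, so they have already returned once. Attendance and withdrawal are different quantities, and holding 50% for one and 20% for the other is not a contradiction. Nor do the documents say whether 50% means half the visits kept or half the children retained.

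A second tempting reading is that counting non-attenders as failures makes success nearly impossible at 50% attendance: P(X ≥ 24 | 35, 0.5) = 0.02. That sets the true rate equal to the null, so the figure is only the type I error of the test and says nothing about sample size.

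Other defences have weight. The study is a pilot. The between-arm comparison is conditional and described as descriptive, and a mixed model can use interim visits. BMI-z power at SD 0.12 stays above target even at 17 to 18. Part of the drop from 0.80 to 0.75 reflects the steps in the exact test; a normal approximation gives 0.79 at n = 28.

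What survives is narrower. The mismatch between 28 and 30 needs no assumption about attendance, and the 20% remains without a stated basis. The hypothesis of better compliance in the Kurbo arms concerns reported app use rather than visit attendance, so it does not supply one.

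**Conclusion.** The point holds in limited form. At the plan's own 20% loss, the primary compliance test has power 0.75, not 0.80. This rests only on the plan's inputs and the exact test that reproduces its figures. The shortfall is modest, but the unqualified power claim is wrong for the primary aim.

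The larger losses are sensitivity scenarios. If half of each arm dropped out completely, compliance power would be 0.52 to 0.57 and between-arm power about 0.56 to 0.62, the latter using only children who complete. If half the visits were missed independently, compliance power would be about 0.77, provided a score from fewer than three visits is accepted, which the plan does not say. The documents do not settle which pattern to expect. BMI-z is affected only if the SD is nearer 0.14.

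**What to change.** 1. **Power and Sample Size.** Replace the unqualified closing claim with evaluable n and compliance power at 20% loss (28; 0.75), 35% loss (22 to 23; 0.52 to 0.65) and 50% loss (17 to 18; 0.52 to 0.57). Label the 35% and 50% rows as sensitivity scenarios, not as the plan's assumption. Give the basis for the 20%, or say that there is none.
2. **Randomization, Allocation and Blinding, and Follow-Up.** Send the same REDCap survey link remotely within a few days of any missed visit, so that the primary compliance outcome no longer depends on attendance. Arrange this before follow-up begins, because missed monthly reports cannot be reliably recovered later.

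The cost is a less favourable stated power, some protocol wording and a few minutes of coordinator time per missed visit. No extra participants are needed. The remote survey does not recover missed BMI-z measurements.
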